**2. OBJECTIVES AND STUDY OUTCOME MEASURES**

**2.1.** Study Objectives

**2.1.1.** Primary Objective(s)

The primary objective for this program is to obtain an understanding and gather information on the percentage of vape users in teens and young adults. This study will include at least 100 individuals, as this will allow us to determine why vaping is so prominent, what causes individuals to be attracted towards this habit, and determine why there is an increasing rate of vaping.

**2.1.2.** Secondary Objective(s)

The secondary objective for this program is to prevent those who do not vape to not begin to partake in this habit and to reduce the percentage pf the target population who are currently vaping, by increasing their knowledge on the dangers of vaping by 10%.

**2.2.** Study Outcome Measures

**2.2.1.** Primary Outcome(s)

We will obtain the percentage of vape users and their reasons for vaping from information gathered from pre-test (Appendix C). Within 6 months, we hope to see a decline in the usage of vapes in the DFW area.

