## **3. STUDY DESIGN**

The time frame for this study will be approximately one month, with the first presentation of the program being in March 2020. This program will be provided to high school and college students within the Dallas Fort Worth metroplex. The program will be implemented by community outreach, as the students will be presented with information about vaping and the resources necessary to prevent or stop vaping from their daily lives. The purpose of this study is to relay and publish data that will support the education of vaping and the many health risks associated with vaping products.

During this program, we will be presenting to 20 to 30 students at a time in a classroom setting, which will allow us to closely interact with participants. This is an anonymous study; therefore, all participants' names will not be listed nor stated in any documentation. In order to accurately complete this anonymously while also calculating our results, students will be asked to list their age, gender, race, and zip code on their survey. This program will be approximately 35 minutes. Participants will be given a pretest (Appendix C) before any information is presented. Students will be given an incentive to complete this program. Below is an outline (Appendix D) of the program:

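### The primary objective says the sample will let the study explain why vaping is rising, but use is asked once and no item ties reasons to change over time

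*Combined protocol and SAP*

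**What the plan says.** Section 2.1.1 (Primary Objective) opens with a descriptive aim, the percentage of teens and young adults who vape. It then makes a claim about what the sample size permits: "This study will include at least 100 individuals, as this will allow us to determine why vaping is so prominent". The same sentence adds what draws people to the habit and ends with the aim to "determine why there is an increasing rate of vaping".

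Section 2.2.1 (Primary Outcome) names the data source: "We will obtain the percentage of vape users and their reasons for vaping from information gathered from pre-test". It adds a hope with no form, visit or analysis attached: "Within 6 months, we hope to see a decline in the usage of vapes in the DFW area".

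Section 3 sets the time scale: "The time frame for this study will be approximately one month, with the first presentation of the program being in March 2020", and "This program will be approximately 35 minutes". The pre-test opens the session and the post-test closes it.

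Section 5.2 provides descriptive summaries, the paired t test, the Wilcoxon signed-rank test and the McNemar test.

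**The concern.** To explain why a rate has risen, one needs the rate and its candidate drivers at two or more times, or a history good enough to rebuild them. A cause offered for an increase must itself have changed. A reason that was as common before the rise as after it can account for the level of use but not for the increase.

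The claim stands in the primary objective, and sections 1.2 and 3 give publication as the purpose of the study. A report that followed 2.1.1 as written would attribute a rise it did not observe to reasons collected at one moment. The sentence also presents the sample size as what makes the explanation possible, although the obstacle is the number of measurement times.

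**Working it through.** **1. The plan's own sample size.** Section 5.1 gives 35 people for a matched-pairs Wilcoxon test with dz = 0.5, 80% power and alpha 0.05. Taking alpha as two-sided (the section does not say) and the asymptotic relative efficiency 3/π = 0.955, the effective n is 35 × 0.955 = 33.4. The noncentrality is 0.5 × √33.4 = 2.89, and the noncentral t gives power 0.801. For 20% attrition, 35 / (1 − 0.20) = 43.75, rounded up to 44. Both figures reproduce. They concern a paired pre/post score. Nothing in 5.1 derives 100 for explaining a trend.

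**2. What the forms measure, and when (Appendix C).**

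| Needed to explain a rise | What is collected |
|---|---|
| Use at two or more times | Pre-test questions 2 (status), 3 (frequency) and 4 (duration); none is on the post-test |
| A later reading of use | Only the already-vaping option of the likelihood item (pre-test 14, post-test 10), in the same session |
| Earlier use, from recall | Question 2 separates current, past and never use; question 4 asks duration |
| Own reasons, now and earlier | Question 11 asks why people in general vape and offers an all-of-these answer; question 12 asks about feeling pressured; neither refers to an earlier time |
| An analysis of trend | None in section 5.2 |

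**3. Can the same-session repeat show change?** In the section 3 timetable, the components between the two tests take 3 + 5 + 3 + 5 + 3 + 5 = 24 minutes. A different answer to the likelihood item after that interval is not a change in use.

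**4. Can recall rebuild a trend?** Question 4 merges vaping with tobacco. Its categories leave gaps between 3 and 6 months and between 6 months and 1 year. Past users are not asked when they stopped. There is therefore no past percentage of vapers to compare with the present one, and no reasons attached to any earlier date.

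**5. Where the rise comes from.** Section 1.1 cites about 12% of high school students in 2016 against 28% in 2019, and a doubling among college students from 2017 to 2018. Both come from outside surveys. Neither citation gives the frequency of reasons in the earlier and later years.

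**6. What n = 100 does buy.** Assume 28% (the section 1.1 figure, used only for scale). The Wilson 95% interval is

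[p + z²/2n ± z√(p(1−p)/n + z²/4n²)] / (1 + z²/n).

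With p = 0.28, n = 100 and z = 1.96:
- centre: (0.28 + 0.0192) / 1.0384 = 0.2881;
- half-width: 1.96 × √(0.002016 + 0.000096) / 1.0384 = 0.0867;
- interval: 20.1% to 37.5%.

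This treats students as independent. They are taught in groups of 20 to 30, so the true interval is likely to be wider. It describes the precision of one percentage and says nothing about change.

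**The case against.** The strongest reply is that 2.1.1 does not claim to measure a rising rate. It takes the rise from the background and asks only why. That is a fair reading, and a reader who inferred that the plan promises to demonstrate a trend would go beyond the text. The cited surveys also cover high school and college students, both of whom are in the target population. The narrower claim still fails, because the reason items have no time dimension. A reason endorsed in March 2020 may have been just as common in 2016.

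A reader might also infer that the forms hold no information at all on change. That is too strong: questions 2 and 4 give some history. It is not adequate for a trend, for the reasons in step 4.

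A reader might expect the report to set the local percentage against the cited 28% and call the difference a trend. The documents plan no such comparison, and section 5.2 contains none.

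Finally, it can be said that the clause is aspirational and that no test, form or sample size depends on it. This is true and it limits the seriousness. It does not remove the point, because the clause sits in the primary objective and is tied to the sample size.

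**Conclusion.** The point holds. As written, part of the primary objective attributes to the study a capability that the design lacks, and no sample size supplies it while use and reasons are asked at one time. The conclusion rests on the placement of the items in Appendix C, the single session in section 3 and the analyses listed in 5.2. The Wilson interval is for scale only and depends on the assumed 28% and n = 100.

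It would be wrong to infer that the whole primary objective is unattainable. The percentage of current users among participants can be estimated, and perceived reasons and peer pressure can be described. Nor does this point show that the section 5.1 calculation is wrong, since it reproduces for the purpose it states. The change should be made, but it is a correction of the stated aim and does not affect data collection.

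**What to change.** In section 2.1.1, delete the clause "determine why there is an increasing rate of vaping" and the statement that 100 individuals allow it. Restate the primary objective along these lines: to estimate, with a 95% confidence interval, the percentage of participating students who report current vaping at the session (pre-test question 2, first option), and to describe perceived reasons for vaping and felt peer pressure at that one time point. Keeping reasons in the objective keeps it in line with 2.2.1, which makes them part of the primary outcome. Describe them as perceived reasons, because question 11 asks about people in general.

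Add a sentence that no conclusion about the cause of a rising rate will be drawn. In section 5.2, name the interval method, for example Wilson, and say whether it allows for classes.

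No change to the forms, sample size or tests is needed. The cost is protocol wording, with IRB review if it is handled as an amendment (section 6.2), and a narrower primary objective. Keeping the explanatory aim would instead require repeated measurement of use and of respondents' own reasons, which is a different study. The hoped-for decline within six months in 2.2.1 and the 5% reduction in section 1.4.1 rest on the same single measurement of use. This wording change does not resolve them, and they need separate attention.

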### 2.2.2. Secondary Outcome(s)

Changes in the degree of understanding will be assessed from the results of the pre- and post-test (Appendix C). In addition, we hope to find the answers to the following questions:

- Is vaping within the student's environment?
- Are the students being socially peer pressured into smoking, and if so how often?
- Are most students forming addictive behaviors towards vaping?
- What are the triggers that cause a student to vape?
- What is their reasoning on why they vape or participate in any smoking products?
- Do members of their close group of friends' vape?
- Are students aware of the serious and long-term side effects of vaping?

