## **IV. Post test**

Program Component	Intro/ Pre-test	History of vapes	Chemical in vapes, and reaction to inside the body	Mental Health	How to change addictive behaviors	Resources	Questions / Recap	Post-test
Brief Description	Introducing the program to the targeted population and having the students take a 5 minute pre-test.	Students will learn about the history of vapes and tobacco.	Students will learn about nicotine and its addictive properties. Students will learn how these things affect the lungs, heart, and teeth	Students will learn how the brain functions and how it reacts to contents in vapes.	Helping the students identify their triggers and learning behaviors to change their point of view.	Providing the students resources within their community	Going back over the main bullet points from the curriculum and letting the students ask questions	Students will take a 5 minute post-test
Duration (in minutes)	5	3	5	3	5	3	5	5

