## 5.2. Statistical Analysis Plan

Descriptive analysis will be performed for all continuous variables. Mean  $\pm$  standard deviation will be presented for normally distributed variables and median  $\pm$  interquartile range will be presented for non-normal variables. Count and proportions will be presented for all categorical variables. All normally distributed continuous outcomes will be analyzed with paired t test and non-normally distributed continuous outcomes will be analyzed with nonparametric Wilcoxon signed-rank test. All Categorical outcomes will be analyzed using McNemar test.

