## Appendix B: Data Collection Tool

## Excel Spreadsheet: Pre-Test

## Excel spreadsheet: Post-Test

## Appendix C

### Pre-Test

1. Do you or have you ever smoked tobacco cigarettes?
  - a. Yes, I currently smoke
  - b. Yes, I smoked in the past
  - c. No, I never smoked
2. Do you or have you ever used a vape pen, e-cigarette, or other vaping products?
  - a. Yes, I currently use these products
  - b. Yes, I have tried these products in the past
  - c. No, I never used these products
3. How often do you vape?
  - a. Everyday
  - b. 3 to 5 times a week
  - c. Once a week
  - d. Few times a month
  - e. Never
4. How long have you been vaping and/or using tobacco products?
  - a. Less than 3 months ago
  - b. 6 months ago
  - c. About 1-2 years ago
  - d. More than 2 years ago
  - e. I never have
5. Using vaping products will help you stop smoking cigarettes?
  - a. True
  - b. False
6. Using vaping products may cause harm to my health?
  - a. True
  - b. False
7. By using vaping products, I am more likely to smoke cigarettes in the future.
  - a. True
  - b. False
8. There are currently \_\_\_\_ million students that use vaping products
  - a. 1 million
  - b. 3.5 million
  - c. 8 million
  - d. 5.3 million
9. Students who vape are \_\_\_\_ more likely to begin smoking cigarettes
  - a. twice

b. four times  
c. five times  
d. ten times

10. There are at least \_\_\_\_ confirmed vape related deaths as of January 21st, 2020  
a. 15  
b. 35  
c. 60  
d. 2

11. People vape because \_\_\_\_  
a. It helps them to relax  
b. Their friends or family vape  
c. They like the taste of it  
d. They think it is safer than tobacco cigarettes  
e. All the above

12. I feel pressured to vape.  
a. Yes  
b. No  
c. Sometimes

13. Effects that vaping has on my body are \_\_\_\_  
a. Decreased brain development  
b. Problems with breathing  
c. Increase heart rate  
d. Higher chance of developing cancer  
e. All the above

14. How likely are you to use vaping products?  
a. Not at all  
b. Not sure  
c. Very likely  
d. I already vape

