## Appendix C

### Post-Test

1. Using vaping products will help you stop smoking cigarettes?
  - a. True
  - b. False
2. Using vaping products may cause harm to my health?
  - a. True
  - b. False
3. By using vaping products, I am more likely to smoke cigarettes in the future.
  - a. True
  - b. False
4. There are currently \_\_\_\_ million students that use vaping products
  - a. 1 million
  - b. 3.5 million
  - c. 8 million
  - d. 5.3 million
5. Students who vape are \_\_\_\_ more likely to begin smoking cigarettes
  - a. twice
  - b. four times
  - c. five times
  - d. ten times
6. There are at least \_\_\_\_ confirmed vape related deaths as of January 21st, 2020
  - a. 15
  - b. 35
  - c. 60
  - d. 2
7. People vape because \_\_\_\_
  - a. It helps them to relax
  - b. Their friends or family vape
  - c. They like the taste of it
  - d. They think it is safer than tobacco cigarettes
  - d. All the above
8. I feel pressured to vape.
  - a. Yes
  - b. No
  - c. Sometimes

9. Effects that vaping has on my body are \_\_\_\_\_

- a. Decreased brain development
- b. Problems with breathing
- c. Increase heart rate
- d. Higher chance of developing cancer
- e. All the above

10. How likely are you to use vaping products?

- a. Not at all
- b. Not sure
- c. Very likely
- d. I already vape

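### The one pressure item cannot give the frequency of peer pressure that section 2.2.2 asks for, and section 5.2, read literally, would also test it for change over a 24-minute session

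*Combined protocol and SAP*

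**What the plan says.** Section 2.2.2 (Secondary Outcomes) opens with change in knowledge: "Changes in the degree of understanding will be assessed from the results of the pre- and post-test (Appendix C"). It then adds seven questions that the study hopes to answer. The second is "Are the students being socially peer pressured into smoking, and if so how often".

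The only item on pressure in Appendix C is "I feel pressured to vape", with the options Yes, No and Sometimes. It is pre-test item 12 and returns with the same wording and options as post-test item 8. By contrast, pre-test item 3, "How often do you vape", has a five-step scale from every day to never.

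Section 5.2 contains two rules that reach this item: "Count and proportions will be presented for all categorical variables" and "All Categorical outcomes will be analyzed using McNemar test". Neither makes an exception for descriptive questions.

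The program table in section 3 puts the pre-test first and the post-test last in one classroom session. No later contact with participants is scheduled.

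**The concern.** There are two linked problems.

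The first is measurement. Section 2.2.2 asks whether peers apply pressure and how often. The item asks whether the student feels pressured, without naming a source, a period or a frequency. It also asks about vaping, where section 2.2.2 says smoking. If the form is used as written, no analysis can supply the missing frequency.

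The second is analysis. The item is categorical, is asked before and after the talk, and serves a question listed under secondary outcomes. On a literal reading of section 5.2 it would be tested for pre/post change. How often friends press a student to vape outside class does not change during one talk, so a significant result could be mistaken for a finding about peer pressure. The item also has three levels, and McNemar's test needs two. The plan does not say how to combine them.

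**Working it through.** **1. Question against item**

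| Element of the question in 2.2.2 | Pre-test 12 / post-test 8 |
|---|---|
| Pressure present | Yes: felt pressure |
| From peers | Not stated |
| Into smoking | Vaping only |
| How often | No scale or recall period; Sometimes is at most a crude grade |

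This part needs no arithmetic and does not depend on how section 5.2 is read.

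**2. Time between the forms.** The durations in the section 3 table are 5, 3, 5, 3, 5, 3, 5 and 5 minutes. They sum to 34, in line with the stated session of about 35 minutes. Without the first (introduction and pre-test) and the last (post-test), 3 + 5 + 3 + 5 + 3 + 5 = 24 minutes.

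**3. The plan's own sample size.** Section 5.1 gives 35 for a Wilcoxon signed-rank test at dz = 0.5, alpha 0.05 and 80% power. A two-sided calculation with the Wilcoxon efficiency for normal data (3/π) returns 35, with power 0.801. Attrition: 35 / 0.8 = 43.75, rounded up to 44. Both figures reproduce, but they size a continuous paired outcome, not this item. The planned enrolment of 100 is used below.

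**4. How small a shift would be significant.** For discordant pairs all in one direction, the exact two-sided McNemar p-value is 2 × (1/2)^d:
- d = 5: 2/32 = 0.0625
- d = 6: 2/64 = 0.031

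Six of 100 students (6%) moving one way is therefore enough.

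**5. Chance of significance under assumed shifts, 100 pairs, exact test**

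| Shift one way | Shift the other way | Chance of p ≤ 0.05 |
|---|---|---|
| 5% | 0% | 0.38 |
| 8% | 0% | 0.82 |
| 10% | 0% | 0.94 |
| 10% | 2% | 0.56 |
| 10% | 5% | 0.18 |
| 5% | 5% | 0.02 |

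These rates are assumptions; the documents give none. Drift that is equal in both directions does not produce excess significant results.

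**6. Effect of the unstated collapse.** Take a hypothetical 100 pairs in which 8 move from Yes to Sometimes, 4 from Sometimes to No, 4 from No to Sometimes, and the rest stay put.
- Yes against the rest: 8 v 0, p = 2/256 = 0.008.
- Yes or Sometimes against No: 4 v 4, p = 1.00.

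The same answers can give opposite conclusions, depending on a choice that the plan leaves open.

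**The case against.** The strongest reply is that the pressure question was meant descriptively. Section 2.2.2 ties pre/post change to understanding and introduces the seven questions separately, as things the study hopes to learn. Section 5.2 also plans counts and proportions, so the pre-test would still give the share of students who feel pressured. No hypothesis or objective predicts a fall in peer pressure. This largely stands: that the item would be tested is an inference from the word covering all categorical outcomes in section 5.2, and one clarifying sentence would settle it. It does not rescue the frequency, which the form never collects.

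A reader might go further and infer that any pre/post difference must be spurious because nothing real can change in 24 minutes. The documents do not support that. The item asks about a feeling, not a count of events. Section 1.1 lists ways of coping with stress and peer pressure as program content, and the section 3 table gives 5 minutes to triggers and changing behavior. Felt pressure could respond to the talk; daily exposure could not.

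For the same reason the repeated item should not serve as a negative control that measures response drift. A negative control must be untouched by the intervention, and the program addresses this very construct.

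Nor do the documents show that the authors intend to report a fall in pressure as a program result. That is a risk of a literal reading, not a stated plan.

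**Conclusion.** The measurement defect is certain on the plain text: one of the seven added questions in section 2.2.2 cannot be answered in full from the data collected. Pre-test counts would give the prevalence of felt pressure to vape, but neither its source nor its frequency.

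The analysis defect is conditional on reading section 5.2 literally. On that reading, the plan tests a three-level item with a two-level test and no stated collapse. A shift would mix changed felt pressure with response drift and could not show a change in the peer pressure met in daily life. The figure of six students in 100 shows how little one-way movement is needed; whether such movement would occur is unknown. The calculations also assume that each student's two anonymous forms can be linked, for which sections 3 and 6.3 give no matching rule.

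The point is modest in scope and cheap to correct, but the item must be corrected before data collection, because the frequency cannot be added afterwards.

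**What to change.** 1. **Appendix C, pre-test item 12.** Ask how often friends or other students pressure the student to vape (adding smoking, to match section 2.2.2), over a stated recall period and on an ordered scale, for example never, less than monthly, monthly, weekly, daily. The recall period must be long enough for the lowest non-zero category to make sense.
2. **Section 2.2.2.** State that this question is answered from the pre-test only.
3. **Section 5.2.** Add a sentence such as: *The peer-pressure item is summarized by counts and proportions from the pre-test; it is not a McNemar outcome and is not evidence of a program effect.*
4. **Post-test item 8.** Either drop it or keep it and report it descriptively only. If it keeps its present wording while item 12 changes, the two are no longer comparable and no pre/post shift can be formed. In neither case should it be used as a negative control.

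The cost is one reworded item and a line each in sections 2.2.2 and 5.2. Dropping item 8 leaves nine post-test items, so the target in objective 3 (section 1.2) of at least eight correct out of ten must be restated for the remaining items. Item 8 asks about the student's own state and has no correct answer, so no scorable content is lost. If the form cannot be changed, the frequency clause should be removed from section 2.2.2 and the result described as the prevalence of felt pressure to vape.

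### Three of the seven questions under Secondary Outcomes (vaping in the student's environment, triggers, close friends who vape) have no direct item on the pre-test or post-test

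*Combined protocol and SAP*

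**What the plan says.** Section 2.2.2 first names change in understanding, assessed from the pre-test and post-test, as a secondary outcome. It continues "In addition, we hope to find the answers to the following questions" and lists seven bullets. Three of them matter most here: "Is vaping within the student's environment", "What are the triggers that cause a student to vape", and the one that begins "Do members of their close group of friends". The other four concern peer pressure and how often it occurs, addictive behaviors, the student's own reasons for vaping or smoking, and awareness of serious long-term effects.

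Section 7.4 says that data come from the paper pre-test and post-test and are then entered in Excel. Sections 3 and 6.3 add age, gender, race, zip code and grade level. No interview, focus group or log of classroom discussion is described.

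Section 2.2.1 makes the percentage of vape users and their reasons for vaping the primary outcome, both taken from the pre-test.

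**The concern.** A question listed among the outcome measures can be answered only if something on the form asks it. If the two tests in Appendix C are the whole data source and no item asks about the student's surroundings, triggers or friends, the study will finish without a direct answer to those three questions.

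The gap could not be repaired afterwards. The study is anonymous (Sections 3, 6.1 and 6.4), so students cannot be contacted again once a session has ended. The gap is also easy to overlook, because several answer options mention friends, relaxation or pressure and look at first sight as if they cover these topics.

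**Working it through.** There is no figure in the plan to reproduce here. The check is an item-by-item match of the seven questions in Section 2.2.2 to the two forms in Appendix C.

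**Inputs.** The pre-test has 14 items: smoking status (1), vaping status (2), vaping frequency (3), duration (4), three true/false statements (5–7), three numeric facts (8–10), why people vape (11), felt pressure (12), effects on the body (13) and likelihood of use (14). The post-test has 10 items, which repeat pre-test items 5–14 in order. It therefore covers no topic that the pre-test lacks.

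| Question in 2.2.2 | Nearest item | What it records | Coverage |
|---|---|---|---|
| Vaping in the environment | none | – | no direct item |
| Peer pressure, and how often | pre 12 / post 8, "I feel pressured to vape" | vaping only; Yes / No / Sometimes | partial |
| Addictive behaviors | pre 2–4, including "How often do you vape" | use, frequency, duration | partial (proxy) |
| Triggers | none | – | no direct item |
| Own reasons | pre 11 / post 7, "People vape because" | beliefs about people in general | partial |
| Close friends who vape | none | – | no direct item |
| Awareness of effects | pre 6, 13 / post 2, 9 | respondent's knowledge | covered |

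**Tally.** No direct item: 3 of 7. Partly covered: 3 of 7. Covered: 1 of 7. 3 + 3 + 1 = 7.

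**Could item 11 or item 12 stand in for the missing three?**

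- Item 11 offers "Their friends or family vape" as one reason why people vape, and closes with an option that takes in all the others. A student with no vaping friends and a student whose friends all vape could tick the same box. The answer does not separate them.
- Item 12 asks about felt pressure. A student may be surrounded by vaping and feel none, so it does not measure exposure.
- The program table in Section 3 has a 5-minute component in which students identify their triggers. It is a teaching component, and no recording of what they say is described.

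**Time available for more items.** The program table gives 5 + 3 + 5 + 3 + 5 + 3 + 5 + 5 = 34 minutes, against a stated length of approximately 35. That leaves 35 − 34 = 1 minute on paper, and the 35 is itself approximate. The pre-test shares its 5 minutes with the introduction.

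**The case against.** The strongest reply is that these bullets are not specified endpoints. The one secondary outcome with a stated assessment is change in understanding. The seven questions follow as hopes, with no analysis of their own in Section 5.2 and no part in the sample size in Section 5.1. This stands, and it limits the weight of the point. It does not remove it: the questions sit under the outcome heading, and a hope with no item behind it cannot be met.

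A second reply is that the forms as printed may not show every field. Appendix B survives only as headings for two spreadsheets. Sections 3 and 6.3 also place demographic details on the forms, and these do not appear in the printed items. Extra fields therefore cannot be fully excluded. Section 7.4 makes them unlikely, because the spreadsheet is filled from the paper tests.

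Three stronger readings are tempting and should be resisted:

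- A reader might infer that the study will hold no information at all on these topics. Items 11 and 12 give weak indirect information on beliefs and felt pressure, so the supportable statement is that there is no direct item.
- A reader might infer that addictive behaviors rest on frequency of use alone. Items 2 and 4 also record current or past use and duration. The protocol does not define the term, so the absence of items on craving or failed attempts to stop is not a departure from it.
- A reader might infer that the primary objective in Section 2.1.1 depends on the three missing questions. That section does not refer to them, and Section 2.2.1 assigns reasons for vaping to the pre-test. The link to the primary outcome runs through the reasons question, which has only a third-person item.

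**Conclusion.** The point holds as a mismatch between the listed questions and the instrument. Three of the seven questions have no direct item on either form, and three more are only partly covered. The partial gap on own reasons deserves the most attention, because the primary outcome in Section 2.2.1 also asks for them and the only relevant item does not ask about the respondent.

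The effect is confined to these descriptive questions. The pre/post knowledge comparison, vaping prevalence (pre-test item 2) and likelihood of future use (pre-test item 14, post-test item 10) do not depend on the missing items.

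The conclusion assumes that the forms printed in Appendix C contain all items on these topics and that nothing said in class is recorded as data. It is worth correcting before the first session because the correction is cheap then and impossible later.

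**What to change.** Before the first session, add three first-person tick-box items to the pre-test only:

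1. the number of close friends who vape;
2. where the student sees people vape;
3. for students who vape, what sets it off and why, ticking all that apply. This also supplies the respondent's own reasons that the primary outcome needs.

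If the team does not want to add them, delete the three questions from Section 2.2.2.

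Item 12 can stay as it is, in which case the part of the peer-pressure question about how often should be treated as not measured. If it is reworded to capture frequency, make the same change to post-test item 8, so that the pair remains comparable for the McNemar analysis in Section 5.2.

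The cost is a revised form, put through the IRB review that Section 6.2 requires, and a longer pre-test: 14 + 3 = 17 items, or 17 + 1 = 18 if pressure to smoke is asked separately. These must fit the 5-minute slot shared with the introduction, with about one unallocated minute in the timetable, so the form should be timed before use. Deleting the questions adds no student time.
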